10. APPENDICES

Not applicable.

11. DESCRIPTION OF GLOBAL AMENDMENT(S)

11.1 GLOBAL AMENDMENT 1

Date of amendment		16 August 2023
EU number		2023-503542-31-00
BI Trial number		1484-0003
BI Investigational Medicinal Product(s)		BI 1584862
Title of protocol		Effect of itraconazole on the pharmacokinetics of a single [REDACTED] dose of BI 1584862 in healthy male subjects (an open-label, two-period, fixed-sequence design study)
Substantial Global Amendment due to urgent safety reasons To be implemented immediately in order to eliminate hazard – IEC / Competent Authority to be notified of change with request for approval.		
		
Substantial Global Amendment e.g. changes in safety or physical or mental integrity of trial subjects, or in interpretation of scientific documents/value of the trial, or in conduct/management of the trial, or change/addition of principal investigators, co-ordinating investigators, or trial sites – implementation only after IEC / Competent Authority approval.		
		
Non-substantial Global Amendment e.g. changes that involve logistical or administrative aspects, or exploratory endpoints only – can be implemented without IEC / Competent Authority approval		
		
Section to be changed	1	Flow Chart
	2	Section 3.3.3 Exclusion criteria
	3	Table 5.2.3: 1 Routine laboratory tests
	4	Section 5.2.6.2.2 AE reporting to the sponsor and timelines
Description of change	1	ECG introduced on Day 2 in Visit 2 and 3
	2	Exclusion criteria no. 27, 28 and 29 introduced
	3	Parameter NT-proBNP added
	4	Reporting timelines rephrased
Rationale for change	1	Requested by health authority / ethics committee
	2	Requested by health authority / ethics committee
	3	Requested by health authority / ethics committee
	4	Requested by health authority / ethics committee

APPROVAL / SIGNATURE PAGE**Document Number:** c40933306**Technical Version Number:**2.0**Document Name:** clinical-trial-protocol-version-02

Title: Effect of itraconazole on the pharmacokinetics of a single [REDACTED] dose of BI 1584862 in healthy male subjects (an open-label, two-period, fixed-sequence design study)

Signatures (obtained electronically)

Meaning of Signature	Signed by	Date Signed
Author-Clinical Trial Leader	[REDACTED]	17 Aug 2023 09:19 CEST
Approval-Clinical Program [REDACTED]		17 Aug 2023 09:55 CEST
Author-Trial Statistician		17 Aug 2023 10:12 CEST
Verification-Paper Signature Completion		17 Aug 2023 13:15 CEST

## 2. LIST OF ABBREVIATIONS

See Medicine Glossary:

<http://glossary>

Term	Definition / description
ALT	Alanine Aminotransferase
ANOVA	Analysis of variance
AST	Aspartate Aminotransferase
AUC 0-∞	Area under the concentration-time curve of the analyte in plasma over the time interval from 0 extrapolated to infinity
AUC 0-tz	Area under the concentration-time curve of the analyte in plasma over the time interval from 0 to the last quantifiable data point
BMI	Body mass index
BP	Blood pressure
CI	Confidence interval
C max	Maximum measured concentration of the analyte in plasma
CSD	Company Standard Displays
CTP	Clinical trial plan
CTR	Clinical trial report
CV	Arithmetic Coefficient of Variation
DILI	Drug induced liver injury
gCV	Geometric Coefficient of Variation
gMean	Geometric Mean
ITZ	Itraconazole
Max	Maximum
Min	Minimum
N	Number non-missing observations
P10	10 th percentile
P90	90 th percentile
PKS	PK parameter analysis set
PR	Pulse rate
Q1	1 st quartile
Q3	3 rd quartile

Term	Definition / description
QD	Quaque die, once daily
R	Reference treatment
RPM	Report Planning Meeting
RAGe	Report Appendix Generator system
SD	Standard Deviation
T	Test treatment
TS	Treated Set
TSAP	Trial Statistical Analysis Plan
ULN	Upper Limit of Normal

### **3. INTRODUCTION**

As per ICH E9 (1), the purpose of this document is to provide a more technical and detailed elaboration of the principal features of the analysis described in the protocol, and to include detailed procedures for executing the statistical analysis of the primary and secondary variables and other data.

This trial statistical analysis plan (TSAP) assumes familiarity with the Clinical Trial Protocol (CTP), including Protocol Amendments. In particular, the TSAP is based on the planned analysis specification as written in CTP Section 7 “Statistical Methods and Determination of Sample Size”. Therefore, TSAP readers may consult the CTP for more background information on the study, e.g., on study objectives, study design and population, treatments, definition of measurements and variables, planning of sample size, randomization.

Study data (including data entered in the RAVE EDC system and external data provided by suppliers) will be stored in a Clinical Data Repository (CDR).

Pharmacokinetic (PK) parameters will be calculated using Phoenix WinNonlin™ software (version 8.1.1 or higher, [REDACTED]) or SAS Version 9.4 (or later version).

The statistical analyses will be performed within the validated working environment CARE, including SAS™ (current Version 9.4, by [REDACTED]), and a number of SAS™-based tools (e.g., macros for the analyses of AE data or laboratory data; Report Appendix Generator system (RAGe) for compilation/formatting of the CTR appendices).

## 4. CHANGES IN THE PLANNED ANALYSIS OF THE STUDY

All analyses as planned in the CTP will be performed and are described in more detail in this TSAP.

To emphasize that the previous and concomitant therapies will be presented by treatment sequence ('BI / ITZ+BI'), the respective sentence of CTP Section 7.2.5 has been rephrased in the TSAP (see [Section 7.2](#)) from "*Previous and concomitant therapies will be presented per treatment group without consideration of time intervals and treatment periods*" to "*Previous and concomitant therapies will be presented for the overall treatment sequence ('BI / ITZ+BI') without consideration of time intervals and treatment periods*".

## 5. ENDPOINTS

### 5.1 PRIMARY ENDPOINTS

#### Section 2.1.2 of the CTP:

*The following pharmacokinetic parameters will be determined for BI 1584862:*

- $AUC_{0-\infty}$  (area under the concentration-time curve of the analyte in plasma over the time interval from 0 extrapolated to infinity)
- $C_{max}$  (maximum measured concentration of the analyte in plasma)

### 5.2 SECONDARY ENDPOINTS

#### 5.2.1 Key secondary endpoint

This section is not applicable as no key secondary endpoints have been defined in the CTP.

#### 5.2.2 Secondary endpoint

#### Section 2.1.3 of the CTP:

*The following pharmacokinetic parameter will be determined for BI 1584862:*

- $AUC_{0-t_z}$  (area under the concentration-time curve of the analyte in plasma over the time interval from 0 to the last quantifiable data point)

### Safety and tolerability endpoints

#### Section 2.2.2.3 of the CTP:

*Safety and tolerability of treatment with BI 1584862 and itraconazole will be assessed based on:*

- Adverse events (including clinically relevant findings from the physical examination)
- Safety laboratory tests
- 12-lead ECG
- Vital signs (blood pressure, pulse rate)

## 6. GENERAL ANALYSIS DEFINITIONS

### 6.1 TREATMENTS

For basic study information on treatments to be administered and selection of doses, refer to CTP Sections 3 and 4.

This trial is designed as an open-label, two-treatment, two-period, fixed sequence design trial in 14 healthy male subjects with a wash-out phase of [REDACTED] between the single dose administrations of BI 1584862 in the two periods.

For details of dosage and formulation see Table 6.1:1 below.

Table 6.1: 1 Treatments and labels used in the analysis

Treatment	Short label
R BI 1584862, [REDACTED]	BI
T Itraconazole oral solution, 200 mg, qd + BI 1584862, [REDACTED]	ITZ+BI

The sequence for “R-T” is named “BI / ITZ+BI” accordingly.

#### Section 1.2.3 of the CTP:

*The Residual Effect Period (REP, the period after the last dose with measurable drug levels and/or pharmacodynamic effects still likely to be present) of BI 1584862 is conservatively assumed to be [REDACTED], i.e. a minimum observation period of at least 10-fold estimated  $t_{1/2}$  has been selected for treatment period 1 (BI 1584862 alone, treatment reference).*

*When given together with itraconazole (Treatment T), it is expected [REDACTED]*

*For the use of itraconazole in Treatment T, the REP is defined as 8 days after last administration of itraconazole in Period 2.*

Based on this, the following study phases will be defined for the analysis of adverse events (AEs):

Table 6.1: 2 Analysis phases for statistical analysis of AEs, and actual treatment for analysis of laboratory data

Study analysis phase	Short Label	Start	End
Screening	Screening	0:00h on date of informed consent	Date/time of administration of BI 1584862 in treatment period 1
On treatment	BI	Date/time of administration of BI 1584862 alone in treatment period 1	
 

 after date/time of administration of BI 1584862 in treatment period 1 

 
 OR Trial termination (0:00 h on the day after trial termination)
Follow-up	FU BI	
 

 after date/time of administration of BI 1584862 in treatment period 1 

 
	Date/time of first administration of itraconazole alone in treatment period 2 OR Trial termination (0:00 h on the day after trial termination) – whatever occurs first
Follow-up	FU ITZ-2	8 days (192 h) after 

 administration of itraconazole in period 2 (End of REP of itraconazole)	Trial termination (0:00 h on the day after trial termination)

### Section 7.2.5 of the CTP:

*Note that AEs occurring after the last per protocol contact but entered before data base lock the trial will be reported to Pharmacovigilance only and will not be captured in the trial database.*

The following AE displays will be provided in the Clinical Trial Report (CTR):

In Section 15.3 and Appendix 16.1.13.1.8 (for ClinicalTrials.gov and EudraCT only) of the CTR displays, the on treatment phase will be analysed (labelled with the short label of the study treatment as in [Table 6.1: 2](#)). The screening and follow-up phases will not be included in this analysis.

The following totals will be provided in addition for Section 15.3:

- A total over all on treatment phases involving BI 1584862 (“**BI Total**”)
- A total over all on treatment phases involving ITZ (“**ITZ Total**”)
- a total over all on treatment phases (“**Total**”)

In Section 15.4 and Appendix 16.2 (Listings) of the CTR displays, the screening period, as well as the follow-up phases will additionally be included.

For detailed information on the handling of the treatments refer to Technical TSAP ADS (analysis data set) plan and Analysis Data Reviewers guide.

## 6.2 IMPORTANT PROTOCOL DEVIATIONS

Data discrepancies and deviations from the CTP will be identified for all treated subjects. Consistency check listings (for identification of deviations of time windows) and a list of protocol deviations (e.g. deviations in drug administration, in blood sampling times, etc.) will be provided to be discussed at the Report Planning Meeting (RPM). At this meeting, all manual deviations identified at the sites by the CRAs and deviations too complex to program will be reviewed by the trial team to decide which are considered important. For definition of important protocol deviations (iPD), and for the process of identification of these, refer to the Boehringer Ingelheim (BI) SOP "Identify and Manage Important Protocol Deviations (iPD)" ([2](#)).

Important protocol deviation (iPD) categories are pre-specified in the iPD specification file (DV domain) ([3](#)). IPDs will be identified no later than in the RPM, and the iPD categories will be updated as needed.

If any iPDs are identified, they are to be summarised into categories and will be captured in the iPD specification file (DV domain) ([3](#)) and in the decision log ([4](#)). Both documents will be stored within the TMF in EDMS.

The iPDs will be summarized and listed in the CTR.

### 6.3 INTERCURRENT EVENTS

This section is not applicable.

### 6.4 SUBJECT SETS ANALYSED

#### Section 7.2.1.1 of the CTP:

*Statistical analyses will be based on the following analysis sets:*

- *Treated set (TS): The treated set includes all subjects who were treated with at least one dose of trial drug. The treated set will be used for safety analyses.*
- *Pharmacokinetic parameter analysis set (PKS): This set includes all subjects in the treated set (TS) who provide at least one PK endpoint that was defined as primary or secondary and was not excluded due to a protocol deviation relevant to the evaluation of PK or due to PK non-evaluability (as specified in Section 7.2.1.2 of the CTP). Thus, a subject will be included in the PKS, even if he contributes only one PK parameter value for one period to the statistical assessment. Descriptive and model-based analyses of PK parameters will be based on the PKS.*

Table 6.4: 1 Subject sets analysed

Class of analysis	Subject set	
	TS	PKS
Primary/secondary and [REDACTED]		X
Safety, treatment exposure & iPD	X	
Disposition, demographics & baseline conditions	X	

## 6.6 HANDLING OF MISSING DATA AND OUTLIERS

Handling of missing data and outliers will be performed as described in the **CTP, Section 7.3:**

**Section 7.3.1 of the CTP:** *It is not planned to impute missing values for safety parameters.*

The only exceptions where imputation might be necessary for safety evaluation are AE dates. Missing or incomplete AE dates are imputed according to BI standards (see “Handling of Missing and Incomplete AE Dates”) (5).

### Section 7.3.2 of the CTP:

*Handling of missing PK data will be performed according to the relevant BI internal procedures.*

*PK parameters that cannot be reasonably calculated based on the available drug concentration-time data will not be imputed.*

Missing data and outliers of PK data are handled according to BI standards (see “Standards and processes for analyses performed within Clinical Pharmacokinetics/Pharmacodynamics” (6) and “Noncompartmental Pharmacokinetic / Pharmacodynamic Analyses of Clinical Studies” (7)).

## 6.7 BASELINE, TIME WINDOWS AND CALCULATED VISITS

The baseline value for laboratory and vital signs analyses is defined as the last measurement before [REDACTED] BI 1584862 or itraconazole drug administration in each treatment period. [REDACTED]

Time windows are defined in **Section 6.1 of the CTP**. Adherence to time windows will be checked via the consistency check listings at the RPM.

Unscheduled measurements of laboratory data and vital signs data will be assumed to be repeat measurements of the most recent scheduled measurement (e.g. for follow-up or confirmation of a particular value). Therefore, unscheduled measurements will be assigned to the planned time point of the previous scheduled measurement.

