1. Subject must be informed and written informed consent obtained prior to starting any screening procedures. Screening procedures include physical examination, check of vital signs, 12-lead ECG, safety laboratory (including drug screening and infectious serology), demographics (including determination of body height and weight, smoking status and alcohol history), medical history, concomitant therapy and review of inclusion/exclusion criteria. Pharmacogenetic samples will be collected if needed.
2. The time is approximate; procedures are to be performed and completed no later than 10 h (admission on [REDACTED] and within 3 h prior to the (next) drug administration.
3. If several actions are indicated at the same time, the intake of meals will be the last action. Meals will be standardised but are not mandatory to be eaten.

4. At the end of study (synonym for End of Trial), the EoS examination includes physical examination, vital signs, ECG, safety laboratory, recording of AEs, and concomitant therapies. Given a subject cannot participate in the 2nd trial period (visit 3), the EoS examination can be performed starting [REDACTED] of visit 2 (1st period).
5. Urine drug screening and alcohol breath test only.
6. AEs and concomitant therapies will be recorded throughout the trial but will be specifically asked for at the times indicated in the [Flow Chart](#) above.
7. Safety laboratory to be taken and to be medically evaluated within 3 days prior to first administration of study drug; this assessment can be omitted if the screening examination is performed on Days -3, -2 or -1.
8. Letters A, B, and C, describe different sets of safety laboratory examinations (see Table [5.2.3: 1](#)).

3.3.4.2	Withdrawal of consent to trial participation	28
3.3.4.3	Discontinuation of the trial by the sponsor	28
3.3.5	Replacement of subjects	29
4.	TREATMENTS	30
4.1	INVESTIGATIONAL TREATMENTS	30
4.1.1	Identity of the Investigational Medicinal Products	30
4.1.2	Selection of doses in the trial	30
4.1.3	Method of assigning subjects to treatment groups	31
4.1.4	Drug assignment and administration of doses for each subject	31
4.1.5	Blinding and procedures for unblinding	32
4.1.6	Packaging, labelling, and re-supply	32
4.1.7	Storage conditions	32
4.1.8	Drug accountability	32
4.2	OTHER TREATMENTS, EMERGENCY PROCEDURES, RESTRICTIONS	33
4.2.1	Other treatments and emergency procedures	33
4.2.2	Restrictions	33
4.2.2.1	Restrictions regarding concomitant treatment	33

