7.2.5 Safety analyses

Safety will be analysed based on the assessments described in Section [2.2.2.2](#). All treated subjects (TS, refer to Section [7.2](#)) will be included in the safety analysis. Safety analyses will be descriptive in nature and based on BI standards. No hypothesis testing is planned.

For all analyses, the treatment actually administered (= treatment at onset) to the subject will be used (any deviations from the assigned treatment will be discussed in the minutes of the Report Planning Meeting).

Treatments will be compared in a descriptive way. Tabulations of frequencies/proportions will be used to evaluate categorical (qualitative) data, and tabulations of descriptive statistics will be used to analyse continuous (quantitative) data.

Measurements (such as ECG, vital signs, or laboratory parameters) or AEs will be assigned to treatments (see Section [4.1](#)) based on the actual treatment at the time of the measurement or on the recorded time of AE onset (concept of treatment emergent AEs). Therefore, measurements performed or AEs recorded prior to [REDACTED] will be assigned to the screening period, those between [REDACTED] and end of REP (see Section [1.2.3](#)) will be assigned to the treatment period.

Events occurring after the REP but prior to [REDACTED] or end of trial termination date will be assigned to 'follow-up'. These assignments [REDACTED] the corresponding time intervals will be defined in detail in the TSAP.

Note that AEs occurring after the last per protocol contact but entered before data base lock the trial will be reported to Pharmacovigilance only and will not be captured in the trial database.

Additionally, further treatment intervals (analysing treatments) may be defined in the TSAP in order to provide summary statistics for time intervals, such as combined treatments, on-treatment totals, or periods without treatment effects (such as screening and follow-up intervals).

Adverse events will be coded using the Medical Dictionary for Regulatory Activities (MedDRA). Frequency, severity, and causal relationship of AEs will be tabulated by treatment, system organ class, and preferred term. SAEs, AESIs (see Section [5.2.6.1](#)), and other significant AEs (according to ICH E3) will be listed separately.

Previous and concomitant therapies will be presented per treatment group without consideration of time intervals and treatment periods.

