### **7.8.2 Laboratory data**

The analyses of laboratory data will be descriptive in nature and will be based on BI standards outlined in “Handling, Display and Analysis of Laboratory Data” (14). Analyses will be based on normalised values, which means transforming to a standard unit and a standard reference range. The original values will be analysed if the transformation into standard unit is not possible for a parameter.

Laboratory data will be analysed qualitatively via comparison of laboratory data to their reference ranges. Values outside the reference range will be flagged in the data listings.

It is the Investigator's responsibility to decide whether a lab value is clinically significant abnormal or not. Clinically significant abnormal laboratory values are identified either in the Investigator's comments or at the Report Planning Meeting at the latest. They will be reported as baseline conditions (prior to first administration of study treatment) or as AEs (after first administration of study treatment).

Descriptive statistics of laboratory data including change from baseline will be calculated by planned time point based on the worst value of the subject at that planned time point (or assigned to that planned time point).

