### **7.8.3 Vital signs**

Descriptive statistics over time including change from baseline will be performed for vital signs (blood pressure and pulse rate). In the listing the change from baseline will also be displayed.

For post-dose measurements of vital signs, descriptive statistics will be calculated by planned time point based on the first value of the subject at that planned time point (or assigned to that planned time point). For baseline value, the last measurement before drug administration in each treatment period will be used.

Clinically relevant findings in vital signs will be reported as baseline conditions (prior to first administration of study treatment) or as AEs (after first administration of study treatment) if judged clinically relevant by the investigator, and will be analysed as such.

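### Unscheduled laboratory values taken after dosing can be tabulated at a pre-dose time point and go missing from the post-dose rows

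*SAP*

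**What the plan says.** **Allocation.** SAP 6.7 sets out the premise: "Unscheduled measurements of laboratory data and vital signs data will be assumed to be repeat measurements of the most recent scheduled measurement". It gives follow-up or confirmation of a value as examples, and concludes that "unscheduled measurements will be assigned to the planned time point of the previous scheduled measurement". No condition about dosing is visible.

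**Laboratory selection.** SAP 7.8.2 computes descriptive statistics, including change from baseline, by planned time point, "based on the worst value of the subject at that planned time point (or assigned to that planned time point"). This is not limited to post-dose time points.

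**Vital signs selection.** SAP 7.8.3 differs. For post-dose measurements, "descriptive statistics will be calculated by planned time point based on the first value of the subject at that planned time point", again including values assigned to it.

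**Baseline.** SAP 6.7 takes the last measurement before "BI 1584862 or itraconazole drug administration in each treatment period". Part of that paragraph is blacked out, but the visible definition rests on time relative to dosing.

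**Treatment label.** Protocol 7.2.5 assigns measurements to treatments "based on the actual treatment at the time of the measurement or on the recorded time of AE onset". The title of SAP Table 6.1: 2 says that the table also gives the "actual treatment for analysis of laboratory data".

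**Schedule.** Flow Chart footnote 7 of the protocol asks for "Safety laboratory to be taken and to be medically evaluated within 3 days prior to first administration of study drug", with a planned time of -74:00 in Visit 2. A scheduled pre-dose row therefore exists. The post-dose laboratory times are not visible.

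**The concern.** The premise that an unscheduled value repeats the last scheduled one suits a retest of a doubtful result. It does not suit a sample drawn because something happened after dosing. The protocol foresees such samples: under the AESI definition (5.2.6.1.4), clinical signs of hepatic injury without available liver results call for those parameters to be measured, in an unscheduled test if need be. That is a new on-treatment observation.

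If it falls before the next scheduled sample, the SAP rules carry it back across the dose. The table then shows an abnormal value where the subject had not yet been treated and an unremarkable row after treatment. Safety and tolerability is a further objective of the trial, potential severe drug-induced liver injury is its only AESI, and 14 subjects are planned, so a single value can move a row mean and set a row maximum.

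**Working it through.** The documents give no figure for this rule, so there is none to reproduce. The check applies the rules literally.

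**Step 1: follow one value.** A scheduled pre-dose sample is taken, the drug is given, an unscheduled sample is drawn, and the next scheduled sample follows.

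- SAP 6.7 moves the unscheduled value to the pre-dose time point.
- SAP 7.8.2 keeps the worse of the two values there. If the unscheduled value is worse, it replaces the true pre-dose value in that row.
- The post-dose row holds only the scheduled value, so the excursion is absent from it and from its change from baseline.
- Baseline is the last value before administration, so it remains the true pre-dose value.
- Protocol 7.2.5 and Table 6.1: 2 label the same value by actual treatment, that is, as on-treatment. It is then on-treatment by phase and pre-dose by planned time point.

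**Step 2: vital signs.** The scheduled value comes first at its time point, so a later value assigned there is not used. The excursion drops out of the summary; it does not displace anything.

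**Step 3: size, with assumed ALT values.** Inputs: 14 subjects (protocol 3.3). Assumed: all scheduled values 25 U/L, and one subject with an unscheduled post-dose value of 200 U/L that resolves before the next scheduled sample.

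- Pre-dose row mean as written: (13 × 25 + 200)/14 = 525/14 = 37.5. True pre-dose mean: 25.0.
- Mean post-dose change as written: 25 − 25 = 0.
- Mean post-dose change with the value counted after dosing: (200 − 25)/14 = +12.5.

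**Step 4: other assumed values.** 14 subjects, pre-dose 25 U/L, scheduled post-dose 30 U/L, one unscheduled post-dose value u. As written, the pre-dose mean is (13 × 25 + u)/14 and the post-dose mean stays at 30. With u counted after dosing, the pre-dose mean is 25 and the post-dose mean is (13 × 30 + u)/14.

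| u (U/L) | Pre-dose mean, as written | Post-dose mean, as written | Post-dose mean, u counted after dosing | Largest post-dose change, as written | Largest post-dose change, u counted after dosing |
|---|---|---|---|---|---|
| 50 | 26.8 | 30 | 31.4 | 5 | 25 |
| 120 | 31.8 | 30 | 36.4 | 5 | 95 |
| 400 | 51.8 | 30 | 56.4 | 5 | 375 |

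As written, the pre-dose maximum equals u in every line. With 12 subjects the pre-dose means are 27.1, 32.9 and 56.2.

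**Step 5: how long the window is.** For liver enzymes, creatinine and bilirubin (set B of protocol Table 5.2.3: 1), it runs from dosing to the first scheduled post-dose sample, whose time is not visible. Haematology, coagulation, electrolytes, glucose, C-reactive protein and NT-proBNP are in sets A and C only (Visits 1 and 4). If the most recent scheduled measurement means that of the same parameter, an unscheduled value of these in either treatment period goes back to screening. If it means the last scheduled laboratory sample of any kind, the reach is shorter; the SAP does not say which.

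**The case against.** The strongest reply is that little depends on this row. Individual values are listed (SAP 7), out-of-range values are flagged, and clinically significant laboratory values after first dosing are reported as AEs (SAP 7.8.2). AEs are assigned to phases by onset. Potential severe liver injury is identified from the subject's own results, not from a table of means. The summary tables also show the median, which stays at 25 in the example of step 3. All of this stands, and it confines the effect to the by-time-point descriptive tables. The internal laboratory standard cited in SAP 7.8.2 might contain an exception for an intervening dose. That cannot be checked, and if it does, the SAP's own wording should say so.

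Three stronger readings are tempting but not supported:

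- **A false fall from baseline.** A reader might subtract the two row means in step 3 (25.0 − 37.5) and infer that the plan would report a fall. Change from baseline uses the last value before administration, which remains 25. The reported change is 0: a rise is missed, and no fall is created.
- **A departure from the protocol.** A reader might infer that SAP 6.7 overrides protocol 7.2.5. The protocol rule concerns the treatment label, which the SAP also follows in Table 6.1: 2; SAP 6.7 concerns the planned time point. What remains is two labels that are not reconciled.
- **A biased worst-value rule.** A reader might infer that setting a worst post-dose value against a last pre-dose value biases the change, and that a first-value rule would cure it. Where high values are retested and there is no drug effect, the shift comes almost entirely from taking the last value as baseline. Changing the post-dose rule would not remove it, and vital signs use the same kind of baseline. Preferring first to worst for laboratory data is a matter of choice.

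**Conclusion.** The point holds within limits. As the SAP reads, an unscheduled laboratory value taken after dosing and before the next scheduled sample of that parameter can appear in a pre-dose or screening row and be absent from the post-dose rows and their change from baseline. The corresponding vital-signs value is left out of the summary.

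In the example, one value of 200 U/L among 14 subjects raises the pre-dose row mean by 12.5 and removes a mean post-dose change of the same size. The ALT values are assumptions, and the effect arises only if such a sample is taken. Its likelihood cannot be judged, because the post-dose laboratory times, part of the baseline paragraph and the internal laboratory standard are not visible. Baseline, listings, AE and AESI reporting and the primary pharmacokinetic analysis are untouched. This is a modest defect in descriptive safety tables, worth correcting because the remedy is cheap.

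**What to change.** In SAP 6.7, state that an unscheduled laboratory or vital-signs value taken after a trial-drug administration is never assigned to a planned time point before that administration. Show it in a separate 'unscheduled, on treatment' row, or as the worst on-treatment value, of the analysis phase in which it was taken, using the phases of Table 6.1: 2. Moving it to the next planned time point is less suitable: it would again carry a wrong time label and, under the first-value rule for vital signs, could displace the scheduled value there.

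Keep the worst-value rule of SAP 7.8.2 for laboratory data. State also whether the most recent scheduled measurement means that of the same parameter.

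The cost is a short SAP wording change and a small change to the derivation of planned time points. The downside is a minor departure from the standard laboratory derivation. A genuine confirmatory retest drawn after a dose would also move to the separate row, which is acceptable because it is an on-treatment value.
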